Body Temperature 		X	X 								X 					X		X 	X 			X	
Body Height		X																					
Pulse rate		X	X 								X 								X 			X	
Body Weight		X	X								X												
Clinical Chemistry 		X									X 								X 				
Hematology 		X									X 								X 				
Thyroid function 		X																					
Urinalysis		X									X 								X 				
Blood sampling for parasite PCR genotyping 			X 																				
Drug administration record for KAF156/LUM-SDF			X								X												
Drug administration record for Coartem ®2			X						X		X							X	X	X			

Period	Screening		Treatment																			Follow-up	
Visit Name	Pre-Screening	Screening	Day 1									Day 2								Day 3			Day 4
Days	-1	-1	1									2								3			4
Time (post-dose)	-	-	0h	1h	3h	4h	5h	6h	8h	12h	24h	25h	27h	28h	29h	30h	32h	36h	48h	60h	68h	72h	
Meal record			X									X								X 			
PK sampling for patient ages 6 to <12 years in Cohort 1 dosed with KAF156/LUM-SDF QD for 2 days 					X			X			X 		X			X			X			X	
PK sampling for patient ages 2 to <6 years in Cohort 1 and 6 months to <2 years in Cohort 2 dosed with KAF156/LUM-SDF QD for 2 days 								X			X 		X			X			X			X	
PK sampling for Coartem ® arm											X 								X 		X		
Electrocardiogram (ECG) in patients dosed with KAF156/LUM-SDF QD for 2 days		X									X 		X			X			X			X	

Period	Screening		Treatment																				Follow-up
Visit Name	Pre-Screening	Screening	Day 1									Day 2									Day 3		Day 4
Days	-1	-1	1									2									3		4
Time (post-dose)	-	-	0h	1h	3h	4h	5h	6h	8h	12h	24h	25h	27h	28h	29h	30h	32h	36h	48h	60h	68h	72h	
Electrocardiogram (ECG) in patients dosed with Coartem®		X																	X 		X		
Overnight Hospital Stay		S	S									S										S	

Period	Follow-up					UNS
Visit Name	Day 5	Day 8	Day 15	Day 29	Day 43 / EOS	UNS
Days	5	8	15	29	43	1 to 43
Time (post-dose)	96h	168h	336h	672h	1008h	-
Pre-screening Informed Consent						
Pre-screening Inclusion criteria						
Demography						
Malaria blood film for asexual parasite counts	X	X	X	X	X	X
Adverse events	X					
Contact IRT	X	X	X	X	X	
Informed consent						
Inclusion / Exclusion criteria						

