### 8.4.2 Electrocardiogram

ECGs should be taken in triplicate within 5 minutes (after 10 minutes rest in the supine position to ensure a stable heart rate according to the ECG investigator manual). The preferred sequence of cardiovascular data collection during study visits is ECG collection first, followed by vital signs, and blood sampling.

The Fridericia QT correction formula (QTcF) must be used for clinical decisions, e.g. at the Screening visit(s) to assess eligibility.

Triplicate 12 lead ECGs are to be collected with ECG machines supplied by the central laboratory and recorded approximately 2 minutes apart. The mean QTcF value for each visit will be calculated from the triplicate ECGs for each participant. Initial manual readout will be done locally in order to detect significant safety findings and allow for immediate response if needed. Local readout will be used for inclusion/exclusion purposes as central readout is not available within 24 hours. Additional, unscheduled, safety ECGs may be repeated at the discretion of the investigator at any time during the study as clinically indicated.

In the event that a clinically significant ECG abnormality is identified at the site (e.g., severe arrhythmia, conduction abnormality of QTcF > 500 ms) the SAE must be reported according to the procedure described in [Section 10.1.2](#). If the patient is hemodynamically compromised, the investigator or a medically qualified person must initiate appropriate safety procedures without delay (for example cardioversion).

If QTcF is > 500 ms or QTcF increases  $\geq 60$  ms from baseline occur at any time, the patient should be assessed at the site and appropriate safety procedures (e.g., blood sampling and electrolyte correction) initiated without delay, if required. In addition two additional ECGs should be collected at 2-min intervals and provided to the central ECG laboratory for confirmation.

Clinically significant abnormalities must be recorded on the relevant section of the medical history/Current medical conditions/AE eCRF page as appropriate.

Any post-dose average QTcF > 500 ms will result in patient discontinuation from the treatment if there is a planned subsequent treatment.

[figure not shown]
Assessments will be done as indicated in the study assessment ([Table 8-1](#)). All ECGs will be assessed centrally by an independent and blinded (with age of patient identified) cardiologist.

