## 10 Safety monitoring and reporting

### 10.1 Definition of adverse events and reporting requirements

#### 10.1.1 Adverse events

An adverse event (AE) is any untoward medical occurrence (e.g., any unfavorable and unintended sign (including abnormal laboratory findings), symptom or disease) in a subject, patient or clinical investigation subject *after providing written informed consent* for participation in the study until the end of study visit. Therefore, an AE may or may not be temporally or causally associated with the use of a medicinal (investigational) product.

[figure not shown]
In addition, all reports of intentional misuse and abuse of the product are also considered an adverse event irrespective if a clinical event has occurred.

The occurrence of adverse events must be sought by non-directive questioning of the patient at each visit during the study. Adverse events also may be detected when they are volunteered by the patient during or between visits or through physical examination findings, laboratory test findings, or other assessments.

Abnormal laboratory values or test results constitute adverse events only if they fulfill at least one of the following criteria:

- they induce clinical signs or symptoms,
- they are considered clinically significant,
- they require therapy.

Clinically significant abnormal laboratory values or test results must be identified through a review of values outside of normal ranges/clinically notable ranges, significant changes from

baseline or the previous visit, or values which are considered to be non-typical in patient with underlying disease. Investigators have the responsibility for managing the safety of individual patient and identifying adverse events. Alert ranges for laboratory and other test abnormalities are included in [Section 16.1](#).

Study drug/treatment includes investigational drugs i.e. KAF156 and LUM-SDF and the comparator Coartem®.

Adverse events must be recorded in the Adverse Events CRF under the signs, symptoms or diagnosis associated with them, accompanied by the following information:

- the Common Toxicity Criteria (CTC) AE grade

If Common Terminology Criteria for Adverse Events (CTCAE) grading does not exist for an adverse event, use

1=mild

2=moderate

3=severe

4=life-threatening (see [Section 10.1.2](#) for definition of SAE)

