### 10.2.4 Cardiac Safety Monitoring

Although QTc extensions and bradycardia are often associated with acute malaria disease and subsequent recovery (fast reduction of fever and heart rate), QTc extensions and bradycardia are also seen as potential side-effects of many anti-malarials. Lumefantrine as part of Coartem®, has shown only modest increase of QTc in a dedicated TQT study, and extensive post-marketing surveillance has not shown signs of cardiotoxicity. ECG results from the previous study CKAF156A2202 where the combination of KAF156 and LUM-SDF was evaluated in acute malaria patients  $\geq 12$  years, did not show clinically relevant QTcF extensions and/or bradycardia following treatment. There was however a mild trend towards higher QTcF change from baseline with increasing exposures. Clinical relevance is unknown.

To ensure patient safety in this study and to fully characterize the cardiovascular safety of the investigational drug, a standardized process for identification, monitoring and evaluation of cardiac events by ECG is followed.

The following categories of notable ECG changes will be assessed during the course of the study (irrespective of whether classified/reported as (S)AE):

- QTcF increase from pretreatment baseline  $\geq 60\text{ ms}$
- QTcF  $> 500\text{ ms}$

Resting heart rate:

- HR (ECG) < 50/min with > 25% decrease from pretreatment baseline or
- HR (ECG) < 50/min associated with symptoms

Cardiac rhythm:

- Any cardiac arrhythmia associated with hemodynamical compromise
- Sustained ventricular tachycardia  $\geq$  30 sec, or ventricular fibrillation

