**Table 16-1 Criteria for notably abnormal vital signs**

Vital sign		Patient age at visit	
		$< 18$ years	$\geq 18$ years
Systolic blood pressure [mmHg]	High	$\geq 95$ th percentile of the age and height group 	$\geq 180$ with increase from updated baseline  of $\geq 20$ mmHg
	Low	$\leq 5$ th percentile of the age and height group 	$\leq 90$ with decrease from updated baseline  of $\geq 20$ mmHg
Diastolic blood pressure [mmHg]	High	$\geq 95$ th percentile of the age and height group 	$\geq 105$ with increase from updated baseline  of $\geq 15$ mmHg
	Low	$\leq 5$ th percentile of the age and height group 	$\leq 50$ with decrease from updated baseline  of $\geq 15$ mmHg
Oral body temperature [°C]	High	$\geq 38.4^{\circ}\text{C}$	$\geq 39.1^{\circ}\text{C}$
	Low	$\leq 35.0^{\circ}\text{C}$	$\leq 35.0^{\circ}\text{C}$

Vital sign		Patient age at visit	
		< 18 years	≥ 18 years
Pulse rate [bpm] 	High	1-6 months > 160	≥120 with increase from updated baseline  of ≥15 bpm
		6-12 months >150	
		12-18 months > 140	
		18-24 months > 135	
		2-3 years > 128	
		3-4 years > 123	
		4-6 years > 117	
		6-8 years > 111	
		8-12 years > 103	
		12-15 years > 96	
		≥ 15 years > 92	
	Low	1-6 months <120	≤50 with decrease from updated baseline  of ≥15 bpm
		6-12 months <110	
		12-18 months < 103	
		18-24 months < 98	
		2-3 years < 92	
		3-4 years < 86	
		4-6 years < 81	
		6-8 years < 74	
		8-12 years < 67	
		12-15 years < 62	
		≥ 15 years < 58	
Weight	High	increase from baseline  of ≥ 2 Body Mass Index (BMI)-for-age percentile categories 	Weight increase from updated baseline  of ≥ 10%
	Low	decrease from baseline  of ≥ 2 BMI-for-age percentile categories 	Weight decrease from updated baseline  of ≥ 10%

Vital sign		Patient age at visit		
		< 18 years	≥ 18 years	
Respiratory rate [breath per minute] 	High	1-6 months	>55	≥30bpm
		6-12 months	>50	
		12-18 months	> 46	
		18-24 months	> 40	
		2-3 years	> 34	
		3-4 years	> 29	
		4-6 years	> 27	
		6-8 years	> 24	
		8-12 years	> 22	
		12-15 years	> 21	
		≥ 15 years	> 20	
	Low	1-6 months	<33	≤ 10bpm
		6-12 months	< 30	
		12-18 months	<28	
		18-24 months	< 25	
		2-3 years	< 22	
		3-4 years	< 21	
		4-6 years	< 20	
		6-8 years	< 18	
		8-12 years	< 16	
		12-15 years	< 15	
		15-18 years	< 13	

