## 16.5 Appendix 5: Cardiac Alert Threshold Values and Actions

**Table 16-6 Cardiac alert threshold values and actions**

	Values	Actions
QTcF	
 
• QTcF > 500.
 
	
 
• If confirmed by two repeat ECG, check and correct the patient's serum potassium and magnesium immediately.
 

Cardiac rhythm	
 
• Sustained ventricular tachycardia lasting 30 sec or more, or ventricular fibrillation, or any hemodynamically compromising cardiac arrhythmia
 
	
 
• Report as SAE to Sponsor and transmit to central vendor immediately for prompt review.
 
• Discontinue patient from study therapy.
 
• Monitor ECG hourly until at least 2 consecutive hourly ECGs performed are back to baseline
 

QTcF	
 
• Increase from baseline <math>\geq 60</math> ms
 
	
 
• If confirmed by two repeat ECG, check and correct the patient's serum potassium and magnesium immediately.
 

Resting heart rate	
 
• HR < 50/min with > 25% decrease from pretreatment baseline verified by ECG
 
	
 
• Report to Sponsor as AE (unless it meets the SAE criteria as described in Section 10.1.2) and transmit to central vendor immediately for prompt review.
 

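### The ECG heart-rate alert is a flat 50/min at every age, so under 8 years it starts only after a fall of at least 32-55%; other safeguards remain, and what is lost is speed and automaticity

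*Protocol*

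**What the plan says.** Protocol Section 10.2.4 notes that QTc prolongation and bradycardia often accompany acute malaria and recovery from it. It adds that QTc prolongation and "bradycardia are also seen as potential side-effects of many anti-malarials". It then lists the ECG changes to be assessed during the study. The first heart-rate entry is "HR (ECG) < 50/min with > 25% decrease from pretreatment baseline or"; the second is a rate below 50/min with symptoms. Neither has an age term.

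The heart-rate row of Table 16-6 (Appendix 5) repeats the first entry: below 50/min with more than a "25% decrease from pretreatment baseline verified by ECG". The action is an AE report to the sponsor (an SAE report if those criteria are met) and immediate transmission to the central vendor for prompt review.

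Table 16-1 (Appendix 1) bands low pulse by age. Its first band that applies to this trial is "6-12 months <110", and the limits then decline with age. It uses 50 only from 18 years. SAP Section 2.8.3.1 likewise counts ECG heart rate against age-specific centiles (SAP Table 2-2).

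Other routes to a slow heart rate are:
- Protocol Section 8.4.2: "Initial manual readout will be done locally in order to detect significant safety findings and allow for immediate response if needed". It also sets an SAE reporting duty that starts "In the event that a clinically significant ECG abnormality is identified at the site". All ECGs are read centrally with the patient's age known, though the central result is not available within 24 hours.
- Protocol Section 10.1.1: investigators review values, and "Alert ranges for laboratory and other test abnormalities are included in" Section 16.1.
- Protocol Section 9.1.1: clinically significant (symptomatic) bradycardia requires study treatment to stop, with no rate cut-off.
- SAP Section 2.8.3.1: additional DMC heart-rate bands, which are also flat across ages but separate 51-60, 61-80 and 81-100 bpm.

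**The concern.** A rate of 50/min is a moderate departure from normal in an adolescent and an extreme one in an infant. The protocol accepts this in Table 16-1, and the SAP accepts it in its centile table, but the alert itself does not. In the youngest children the only heart-rate rule that starts a report without a judgement call is set so low that it responds only to a very large fall.

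The ECG trigger also covers times that scheduled pulse does not. In Table 8-2, pulse at 0 and 24 h is taken before dosing (footnote 11), and the next pulse is at 48 h. The row "Electrocardiogram (ECG) in patients dosed with KAF156/LUM-SDF QD for 2 days" has ECGs at 27 and 30 h, which is 3 and 6 h after the second dose. Table 8-3 adds ECGs at 51 and 54 h, again with no scheduled pulse at those times.

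The main group is Cohort 2: about 80 children of 6 months to under 2 years, randomized 1:1, so about 40 on KAF156/LUM-SDF. The ECG experience cited in Section 10.2.4 comes from patients of 12 years and older. Section 4.5 expects data for 2 to under 12 years (fasting) before Cohort 1 starts. Section 4.2 describes that study as dosing patients over 2 years, so it gives no such data for Cohort 2. Cohort 1 children under 8 years are affected to a lesser degree; their number is not stated.

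**Working it through.** The plan states no derived figure for this alert, so there is nothing to reproduce first. The inputs are the 50/min cut-off and the 25% clause (Section 10.2.4, Table 16-6) and the low (L) and high (H) pulse limits of Table 16-1.

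**Step 1. Smallest fall that reaches 50/min.** From the lowest in-range baseline it is 1 - 50/L. From a baseline at the upper limit, nearer to a febrile child, it is 1 - 50/H.

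| Age | L | 50/L | Fall from L | H | Fall from H |
|---|---|---|---|---|---|
| 6-12 months | 110 | 45% | 54.5% | 150 | 66.7% |
| 12-18 months | 103 | 49% | 51.5% | 140 | 64.3% |
| 18-24 months | 98 | 51% | 49.0% | 135 | 63.0% |
| 2-3 years | 92 | 54% | 45.7% | 128 | 60.9% |
| 3-4 years | 86 | 58% | 41.9% | 123 | 59.3% |
| 4-6 years | 81 | 62% | 38.3% | 117 | 57.3% |
| 6-8 years | 74 | 68% | 32.4% | 111 | 55.0% |
| 8-12 years | 67 | 75% | 25.4% | 103 | 51.5% |
| 12-15 years | 62 | 81% | 19.4% | 96 | 47.9% |
| 15 years and over | 58 | 86% | 13.8% | 92 | 45.7% |

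From 12 years the column from L falls below 25%, so there the 25% clause sets the requirement at low baselines. SAP Table 2-2 gives almost the same picture: its 10th percentiles of 114 (6 to under 9 months) and 109 (9 to under 12 months) give 56.1% and 54.1%, and the values from 12 months to under 6 years are identical.

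**Step 2. When the 25% clause binds.** A 25% fall lands on 50/min from a baseline of 50/0.75 = 66.7. The clause adds a condition only below that baseline. Every low limit under 8 years is 74 or more, so it never binds for an in-range child of that age. At 8-12 years (limit 67) the two conditions practically coincide. Where the clause does not bind, the symptom entry adds nothing either, because it also requires a rate below 50/min.

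**Step 3. Examples.** A 10-month-old slowing from 150 to 60 without symptoms has fallen by 90/150 = 60% and does not meet the alert. An infant at 55/min with symptoms meets neither heart-rate entry.

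**Step 4. Size of the contrast with adolescents.** From low baselines the comparison is 54.5% with just over 25%, about twofold. From upper-limit baselines, for children under 6 years, it is 57.3/47.9 = 1.20 to 66.7/45.7 = 1.46.

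**Step 5. An illustrative banded limit.** At 12-15 years, 50/min is 50/62 = 0.806 of the Table 16-1 limit. Applying that ratio to L below 12 years gives 88.7, 83.1, 79.0, 74.2, 69.4, 65.3, 59.7 and 54.0, or about 89, 83, 79, 74, 69, 65, 60 and 54. From the upper limit, the unrounded values need falls of 41-44% under 6 years, close to the 46-48% in adolescents. The 25% clause binds again at the low end: from 110 the alert would need a rate below 0.75 x 110 = 82.5, which is under 89. An infant slowing with recovery from 150 to 109 (27%) or to 90 (40%) would not alert; 150 to 88 (41%) would.

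**The case against.** The strongest reply is that little depends on this trigger. It starts a report and a prompt review; it does not stop treatment. Sites read ECGs locally and must report a clinically significant abnormality without needing symptoms, and an infant falling from 150 to 60 is an obvious candidate. Symptomatic bradycardia stops treatment at any rate, hemodynamically compromising arrhythmia is a separate alert, and children are in hospital until Day 4. The DMC sees heart-rate bands above 50, and Cohort 2 enrollment pauses while the DMC reviews its first 24 patients. All of this stands, and it limits the point to speed and automaticity. It does not repair the rule, because these routes depend on judgement or come later. The examples that Section 8.4.2 gives for the SAE duty do not name slowing as such.

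A second reply is that Table 16-1 serves another purpose. From 12 months its low limits equal the SAP's 10th percentiles, and an expedited alert should sit well below a 10th percentile. That is fair, and the percentages in the table do not show how many relevant cases would be missed. But the same 50/min sits at 81% of the limit at 12-15 years and at 45% in infants, so its strictness changes with age without a stated reason.

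Third, Section 10.2.4 reports no clinically relevant bradycardia in CKAF156A2202, and it expects slowing as malaria resolves. Both are true. The first concerns patients of 12 years and older; the second is a reason to keep the 25% clause and to choose the limits with care.

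A reader might infer that bradycardia in infants would go undetected. The documents do not support that, given the routes above.

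**Conclusion.** The concern holds in a limited form and is minor. The alert is flat across ages while the protocol's own pulse limits are not. From an in-range baseline it needs a fall of at least 49-55% under 2 years, 38-46% at 2 to under 6 years and 32% at 6-8 years. In those ages the 25% clause does nothing, and the automatic report and prompt central review can be expected to start rarely. How rarely cannot be given as a number, because the documents contain no heart-rate distribution.

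The conclusion assumes that Table 16-1 pulse limits are a fair yardstick for ECG heart rate, which the near-identical SAP Table 2-2 supports, and that baseline is within range. From a high, febrile baseline the contrast with adolescents shrinks to about 1.2- to 1.5-fold.

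A reader might also take the 50/62 scaling as a threshold the documents establish. They do not; the right values are a clinical choice.

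**What to change.** In Section 10.2.4 and the heart-rate row of Table 16-6, replace 50/min with limits banded by age and tied to Table 16-1 for all bands below 12 years. Keep the requirement of a fall of more than 25% or symptoms. The sponsor's cardiac safety experts should confirm the values. One illustration is below 89, 83, 79, 74, 69 and 65 for the six bands from 6-12 months to 4-6 years, about 60 at 6-8 years and 54 at 8-12 years, then 50 from 12 years. Stopping the bands at 6 years would leave out 6-8 years and drop the limit from 65 to 50 at the sixth birthday.

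This changes a safety alert, so it needs a protocol amendment with the approvals in Section 14.1. It needs no new visits or data. The downside is some added alerts during recovery from fever, in a number that cannot be estimated from the documents.

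A small related edit: for repeated ECGs, the by-visit rule in SAP Table 5-7 takes the higher value as the worse one for each measurement. For slowing, the lower heart rate should be used. Counts of notable abnormalities are unaffected, because the next row of that table already takes the most extreme value in the window.

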## **11 Data Collection and Database management**

### **11.1 Data collection**

Designated investigator staff will enter the data required by the protocol into the eCRFs. The eCRFs have been built using fully validated secure web-enabled software that conforms to 21 Code of Federal Regulation (CFR) Part 11 requirements; investigator site staff will not be given access to the EDC system until they have been trained. Automatic validation programs check for data discrepancies in the eCRFs, allow modification and/or verification of the entered data by the investigator staff.

The investigator/designee is responsible for assuring that the data (entered into eCRF) is complete, accurate, and that entry and updates are performed in a timely manner. The Investigator must certify that the data entered are complete and accurate

After final database lock, the investigator will receive copies of the patient data for archiving at the investigational site.

[figure not shown]
All data should be recorded, handled, and stored in a way that allows its accurate reporting, interpretation, and verification.

### **11.2 Database management and quality control**

Novartis personnel (or designated Contract Research Organization (CRO)) will review the data entered by investigational staff for completeness and accuracy. Electronic data queries stating the nature of the problem and requesting clarification will be created for discrepancies and missing values and sent to the investigational site via the EDC system. Designated investigator site staff are required to respond promptly to queries and to make any necessary changes to the data.

Concomitant treatments and prior medications entered into the database will be coded using the World Health Organization (WHO) Drug Reference List, which employs the Anatomical Therapeutic Chemical classification system. Medical history/current medical conditions and adverse events will be coded using the Medical Dictionary for Regulatory Activities (MedDRA) terminology.

Randomization codes and data about all study treatment(s) dispensed to the patient and all dosage changes will be tracked using an Interactive Response Technology (IRT). The system will be supplied by a vendor, who will also manage the database. The data will be sent electronically to Novartis (or a designated CRO) at specific timelines.

Each occurrence of a code break via IRT will be reported to the clinical team and monitor. The code break functionality will remain available until study shut down or upon request of Novartis.

[figure not shown]
Once all the necessary actions have been completed and the database has been declared to be complete and accurate, it will be locked and the treatment codes will be made available for data analysis/moved to restricted area to be accessed by programmer and statistician. Any changes to the database after that time can only be made after written agreement by Novartis development management.

